### 1.8.2 Secondary

- Assess the effect, on WHO bleeding score, of increasing doses of allogeneic Thrombosomes.
- Assess the effect of increasing doses of allogeneic Thrombosomes on measures of coagulation.

\* Note: Only a subset of patients with Grade 1 bleeding who have either epistaxis, hematuria, oral petechiae, oropharyngeal bleeding, or bleeding at invasive or other wound sites.

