### **1.9.9 Safety Endpoints**

Primary: The occurrence and frequency of AEs, SAEs, and thromboembolic events as determined by clinical signs and symptoms, physical exam including neurological assessment, and laboratory studies.

Secondary:

- Describe the effect of increasing doses of allogeneic Thrombosomes on bleeding including changes in WHO bleeding grade.
- Describe the effect of increasing doses of allogeneic Thrombosomes on coagulation measures.

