## 2 STUDY OBJECTIVES AND ENDPOINTS

### 2.1 Study Objectives

#### 2.1.1 Primary Objective

The primary objective of this study is to assess the effect of escalating infusion doses of Thrombosomes on the safety of actively-bleeding, thrombocytopenic patients.

Three dose levels, including 5 mL ( $9.45 \times 10^7$  particles/kg or 165 thrombin generation potency units [TGPU] per kg), 10 mL ( $1.89 \times 10^8$  particles/kg or 330 TGPU/kg), and 20 mL ( $3.78 \times 10^8$  particles/kg or 660 TGPU/kg), will be studied across 3 sequentially enrolled patient cohorts. Incidence of treatment-emergent adverse events (TEAEs) and serious adverse events (TESAEs), application of suspension or stopping rules, and abnormality or worsening in measures of bleeding severity, coagulation, hematology, serum chemistry, vital signs, and cardiac, physical, and neurologic statuses will be used as indicators of safety.

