## 2.2 Study Endpoints

### 2.2.1 Primary Endpoints

Several primary endpoints will be quantified per patient cohort (i.e., by dose level), as well as overall (i.e., across all 3 dose levels):

- Overall frequency of (and number and percentage of patients who experience) TEAEs and TESAEs, including serious adverse drug reactions and treatment-related events specifically defining the study's suspension and stopping rules (i.e., thromboembolic events, acute lung injury, anaphylaxis, and death).
- Numbers and percentages of patients by highest WHO bleeding severity grade at baseline and post-baseline time-points, by highest severity grade at post-baseline time-points relative to baseline (allowing for assessment of shift), by both highest severity grade and bleeding site at baseline and post-baseline time-points, and by indication of a maximum severity grade  $\geq 2$  across bleeding sites at post-baseline time-points.
- Numbers and percentages of patients by grade-level change in WHO bleeding severity (e.g., -2, -1, 0, +1, +2, +3) from baseline to post-baseline time-points for the patient's most severe bleeding site at baseline, by indication of increased bleeding severity from baseline to post-baseline time-points for the patient's most severe bleeding site at baseline, and by indication of newly-developed bleeding sites from baseline to post-baseline time-points.
- Statistics describing (and/or graphics showing) central tendency and variability in coagulation, hematology, and serum chemistry measures across patients at baseline and post-baseline time-points, allowing for assessment of directional change in measures over time.
- Number and percentage of patients who shift from normal or clinically non-significant abnormal findings to clinically significant abnormal findings in coagulation, hematology, or serum chemistry measures between baseline and post-baseline time-points.
- Statistics describing central tendency and variability in vital signs, oxygen saturation (per pulse oximetry), and select 12-lead electrocardiogram (EKG) measures across patients at baseline and post-baseline time-points.
- Number and percentage of patients who shift in category of overall EKG interpretation from normal or clinically non-significant abnormal to clinically significant abnormal between baseline to post-baseline time-points.

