## 6.3 Data Derivations based on Timing

For a given date within the screening period, the sequence number identifying the study day will be computed as the relevant screening date minus the date of Day 1 (i.e., screening date – date of Day 1). For a given date on/following infusion with Thrombosomes, the sequence number identifying the study day will be computed as the relevant infusion (or post-infusion) date minus

the date of Day 1 plus 1 day (i.e., infusion or post-infusion date – date of Day 1 + 1) to allow for inclusion of Day 1 within the computed period.

The following will define prior medication use versus concomitant medication use:

- Prior medication – any medication last used by a patient within the 4 weeks immediately preceding the date of Thrombosomes infusion. Anti-coagulant medications represent an exception, with the applicable range in dates ending at 48 hours before infusion.
- Concomitant medication – any medication taken on or after the date of Thrombosomes infusion through the Day-6 visit. Anti-coagulant medications represent an exception, defined as concomitant if taken at any time during the 48 hours preceding infusion through the Day-6 visit.

Baseline values for all assessment variables will be based on data collected during the latest assessment procedure performed prior to infusion with Thrombosomes. Unless otherwise specified, the change-from-baseline (CFB) value corresponding to any quantitative post-infusion assessment variable will be calculated by subtracting the baseline assessment value from the relevant post-infusion assessment value. If either the baseline or post-infusion assessment value is missing, then the CFB value will also be set to missing.

Pre-treatment AEs and treatment-emergent AEs (TEAEs) will adhere to straightforward definitions, with pre-treatment events occurring prior to start of the Thrombosomes infusion on Day 1 and treatment-emergent events occurring at or following the start of infusion.

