### 8.2 WHO Bleeding Severity Scores

Within multiple tables, the numbers and percentages of patients will be presented by highest WHO bleeding severity score (no bleeding/grade 0, grade 1, grade 2, grade 3, or grade 4), with "highest severity score" defined as the score associated with the most severe bleeding site (given documentation of multiple sites) for the nominal time-point of interest. This distribution of highest WHO bleeding severity scores not only will be presented by nominal time-point but also will be presented by post-baseline time-points relative to baseline time-point (to allow for assessment of shift) and by both bleeding site and time-point. Differences between patient cohorts (dose levels) in the proportion of the study population showing grade 2 or higher bleeding severity for the most severe bleeding site will be tested for statistical significance per time-point using Fisher's exact test, with results displayed in a single table. To facilitate visual examination of trends, 1 or more of the summaries described above may be presented within supplementary clustered bar charts or line chart overlays.

The numbers and percentages of patients will also be presented by grade-level change in WHO bleeding severity (-2, -1, 0, +1, +2, and +3) from baseline to post-baseline time-points for the patient's most severe bleeding site at baseline, by indication of increased bleeding severity from baseline to post-baseline time-points for the patient's most severe bleeding site at baseline, and by

indication of development of new bleeding sites from baseline to post-baseline time-points. Lastly, the details of all WHO bleeding assessments will be presented in a patient-level data listing. To facilitate, within this listing, visual examination of possible post-infusion changes in bleeding severity or number of bleeding sites as associated with protocol-defined windows for the timing of infusion relative to screening (i.e., within 24 hours [as stipulated in CSP v1.1] vs. within 4 days [as stipulated in CSP v2.0+]), the data listing will be sorted first by the screening assessment dates of patients and then, within individual patients, by assessment date.

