Importantly, patients with multiple bleeding sites may show tied bleeding severity scores. For summaries in which patients' highest severity scores will be reported independently by visit or by visit and bleeding site (as described in the first paragraph of this section), tied scores will have no consequence and the highest score reported will simply represent multiple bleeding sites. However, for summaries in which each patient's most severe bleeding site is selected at baseline and tracked across subsequent time-points (as described in the paragraph immediately above), bleeding site selection will depend on continued comparison of severity scores across subsequent time-points until the tie in severity score is broken. For example, if a tie in severity score exists at baseline, the bleeding sites involved in the tie will be compared using scores recorded at the patient's next visit (i.e., 1-hour post-infusion) and the site of highest severity will be selected. If scores are still tied at 1 hour following infusion, then scores from the 6-hour post-infusion visit will be compared, and so forth.

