### **14.3.3 WHO Bleeding Severity Scores**

Table 14.3.3.1	Summary of Highest WHO Bleeding Severity Scores by Visit – Safety Population
Table 14.3.3.2	Summary of Highest WHO Bleeding Severity Scores by Bleeding Site and Visit – Safety Population
Table 14.3.3.3	Shift from Baseline in Highest WHO Bleeding Severity Score – Safety Population
Table 14.3.3.4	Between-Cohort Differences in WHO Bleeding Severity Scores of at least Grade 2 – Safety Population
Table 14.3.3.5	Post-Infusion Grade-Level Changes in Bleeding Severity Score for Most Severe Bleeding Site at Baseline – Safety Population
Table 14.3.3.6	Subjects with Increased Post-Infusion WHO Bleeding Score for Most Severe Bleeding Site at Baseline – Safety Population
Table 14.3.3.7	Subjects with Post-Infusion Development of New Bleeding Sites – Safety Population

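### SAP 8.2 uses post-infusion scores to break baseline ties for the tracked bleeding site, so Tables 14.3.3.5 and 14.3.3.6 lean toward worsening among tied patients whose sites diverge

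*SAP*

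**What the plan says.** SAP 8.2 tabulates patients "by grade-level change in WHO bleeding severity (-2, -1, 0, +1, +2, and +3) from baseline to post-baseline time-points" for the site that was most severe at baseline. SAP 2.2.1 lists that summary among the primary endpoints, and also counts patients "by indication of increased bleeding severity from baseline to post-baseline time-points for the patient's most severe bleeding site at baseline". These become Tables 14.3.3.5 ("Post-Infusion Grade-Level Changes in Bleeding Severity Score for Most Severe Bleeding Site at Baseline") and 14.3.3.6.

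The last paragraph of SAP 8.2 covers patients with two or more sites at the same top grade. For these two summaries the tied sites are compared on "scores recorded at the patient's next visit (i.e., 1-hour post-infusion) and the site of highest severity will be selected". If they are still level at 1 h, the 6 h scores are compared, and so on.

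Four other places bear on the point:

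- SAP 6.3: "Baseline values for all assessment variables will be based on data collected during the latest assessment procedure performed prior to infusion with Thrombosomes". It also sets a change from baseline to missing when either value is missing.
- SAP 2.1.1 counts "abnormality or worsening in measures of bleeding severity" among the indicators of safety.
- Protocol 1.8.2 has as a secondary objective: "Assess the effect, on WHO bleeding score, of increasing doses of allogeneic Thrombosomes". Protocol 1.9.9 has a matching endpoint, the effect of increasing doses "on bleeding including changes in WHO bleeding grade".
- Protocol 1.9.3 has every bleeding site graded at screening, at rescreening where it applies, at baseline, and at 1 h, 6 h, 24 h and 6 days. It accepts that some sites cannot be reassessed after infusion.

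**The concern.** A site labelled as the baseline site is chosen by what happens to it after treatment, and the choice always goes to the site that did worse. At the visit that breaks the tie, the recorded change is the largest change among the tied sites. It is not the change at a site named in advance.

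Two things are at stake. First, Table 14.3.3.5 reports improvement (-2, -1) as well as worsening, and the protocol asks about change in WHO grade in either direction. The rule trims the improvement categories and swells the worsening ones. Second, one table mixes two quantities: a single site for untied patients, and a site picked by its outcome for tied patients. If the number of tied patients differs by cohort, the distortion differs by dose, and the SAP does not report tie counts.

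There is also a small gap. SAP 8.2 does not say what happens when a tied site has no post-infusion score, which Protocol 1.9.3 allows and which SAP 6.4 would not impute.

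**Working it through.** The plan states no figure for this rule, so there is nothing to reproduce. Protocol 1.13 and SAP Section 4 give 8 patients per cohort with no statistical derivation. Per-site rates, number of tied sites, share of patients tied and correlations are all assumptions here. Changes are taken as one grade.

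**1. Direction at the first post-infusion visit.** With k tied sites, each worsening with probability w and improving with probability i:

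- recorded worse = P(at least one site worsens) = 1 - (1 - w)^k if sites are independent;
- recorded improved = P(all sites improve) = i^k if independent.

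For w = i = 20%:

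- k = 2: 1 - 0.8² = 36% worse and 0.2² = 4% improved.
- k = 3: 1 - 0.8³ = 49% worse and 0.2³ = 1% improved.
- A site fixed before infusion gives 20% and 20%.

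For w = 10%, i = 30%, k = 2: 19% worse and 9% improved. The mean change is 0.19 - 0.09 = +0.10, against 0.10 - 0.30 = -0.20 for a fixed site. If tied sites always move together, the rule changes nothing.

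**2. Cohort effect at 1 h, slow onset.** Take i = w = 10% at 1 h and two tied sites. Recorded improved is P(both improve). Recorded worsened is 0.20 - P(both worsen). Correlation is on a bivariate normal latent scale. In a cohort of 8 with m tied, the expected number improved is (8 - m) × 0.10 + m × recorded. The gap between m = 1 and m = 4 is therefore 3 × (0.10 - recorded).

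| Between-site correlation | Recorded improved | Recorded worsened | Gap in improved, 1 v 4 tied | Cohort worsened, 1 v 4 tied |
|---|---|---|---|---|
| 0 | 0.010 | 0.190 | 3 × 0.090 = 0.27 patient | 11.1% v 14.5% |
| 0.5 | 0.032 | 0.168 | 3 × 0.068 = 0.20 patient | 10.8% v 13.4% |
| 0.8 | 0.056 | 0.144 | 3 × 0.044 = 0.13 patient | 10.5% v 12.2% |

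**3. Tied patients at 24 h.** Assume two tied sites, improvement of 10% at 1 h, 25% at 6 h, and 50% at 24 h and Day 6, with 10% worsened throughout. I applied the SAP rule visit by visit until the tie broke, in 1,000,000 simulated pairs with latent normal scores. Between-site and visit-to-visit correlations ran from 0 to 0.8.

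- Recorded improved at 24 h: from 0.272 (between-site 0, visit-to-visit 0.8) to 0.437 (0.8 and 0).
- Recorded worsened at 24 h: from 0.181 to 0.127 at the same two settings.
- A site fixed before infusion: 0.50 and 0.10.

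**4. What the rule follows later.** Once the tie breaks, one site is followed for good. In the same simulation that site was not the worst of the tied sites in about 1-20% of tied patients at 24 h and 2-25% at Day 6.

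**5. What is untouched.** Tables 14.3.3.1 to 14.3.3.3 use the highest score at each time-point (14.3.3.2 by site). Table 14.3.3.4 (Fisher's exact test) uses the highest grade. Table 14.3.3.7 counts new sites. None uses the tie-break.

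**The case against.** The best defence is that following the worse site is the cautious choice for a safety indicator, and SAP 2.1.1 uses bleeding severity as one. The SAP rests efficacy on hematology and transfusions, and its Section 11 discloses the move away from WHO grade. Both tables are descriptive, and every WHO assessment appears in the patient listing. All of this stands and limits the weight of the point. It does not rescue the rule. Worst-site reporting already exists in Tables 14.3.3.1 and 14.3.3.3. After the tie breaks, the followed site need not stay the worst, so the rule is not a consistent worst-case measure. Table 14.3.3.5 also reports improvement.

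A reader might infer more than the documents support:

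- *That SAP 6.3 is breached.* It governs baseline values, and tied sites share the same value. The choice between sites departs from the principle, not from the text.
- *That a patient whose tie breaks can never be recorded as improved at that visit.* This holds only for one-grade changes. SAP 8.2 allows -2, so a -2/-1 pair breaks the tie and is recorded as improved.
- *That the first-visit cohort gap is larger.* Putting 50% improvement in at 1 h with independent sites gives 3 × (0.50 - 0.25) = 0.75 of a patient. Nothing in the documents supports so early a response, and even that is under one patient.

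**Conclusion.** The point holds for tied patients whose sites diverge. At the visit that breaks the tie, the direction is certain: worsening is overstated and improvement understated. At later visits the bias persists or fades, depending on how strongly a site's scores are correlated over time. The tilt works against the product.

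The size is illustrative only. Under the slow-onset assumptions, improvement among tied patients at 24 h is recorded as about 27-44% instead of 50%, and worsening as 13-18% instead of 10%. At 1 h the difference between cohorts with 1 and 4 tied patients is about 0.13-0.27 of a patient. There is no bias where no patients are tied or where tied sites move together.

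A reader might conclude that the trial's safety decisions or its between-cohort test are compromised. The documents do not support that. The SAP attaches no test to either table, neither feeds the suspension or stopping rules, and the highest-score, shift and Fisher tables do not use the rule. This is a modest flaw in listed primary endpoints, worth correcting because the correction is cheap.

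**What to change.** Amend SAP 8.2 before database lock:

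1. Break baseline ties with pre-infusion information only. First take the site with the higher WHO grade at the most recent screening or rescreening assessment. If still tied (for example, when neither site was bleeding then), use a fixed site order or a seeded random order written in the SAP.
2. If the chosen site is not reassessed at a visit, its change is missing at that visit, in line with SAP 6.3 and 6.4. No other tied site is substituted.
3. Footnote the number of tied patients per cohort in Tables 14.3.3.5 and 14.3.3.6.
4. If the current rule is kept as a sensitivity table, label it *site selected by first post-infusion divergence*. Calling it the worst of the tied sites would be wrong, as step 4 of the working shows.

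The cost is SAP wording, two footnotes and at most one extra table. The site grades at screening are already collected, so no data item or CRF changes, and no test is removed.

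The drawback is that a site chosen in advance may be the tied site that later does better, while an equally severe one worsens. Tables 14.3.3.1, 14.3.3.2, 14.3.3.3 and 14.3.3.7 and the patient listing still show worst-site, by-site and new-site bleeding.

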### 8.3 Clinical Laboratory Assessments

Laboratory assessments to be used in safety monitoring will include coagulation, hematology, and serum chemistry measures. For each assessment type, descriptive statistics summarizing the raw and CFB values of all measures (or select measures, see Hematology below) will be provided in 2 tables. As the Wilcoxon signed rank test will be used to test for difference between baseline and post-baseline values, the P-values derived during testing will be displayed within these tables, adjacent to corresponding CFB values. In 2 additional tables, the numbers and percentages of patients who show abnormal results and who show changes (shifts) from baseline in interpreted results (normal, abnormal non-clinically significant, and abnormal clinically significant) will be summarized per measure and visit. Measures corresponding to each assessment type will include those listed below, given sufficient data available for descriptive analysis (i.e., minimally 3 data points per computed statistic for each of 2 or more visits).

- **Coagulation:** PT, INR, aPTT, D-dimer, fibrinogen, TAT, PF 1+2, TEG (R time, K time, MA, angle), ROTEM (CT, CFT, angle, MCF), and TGA (lag time, time to peak, thrombin peak height, ETP)
- **Hematology:** WBC, RBC, hemoglobin, hematocrit, platelets, MPV, neutrophils, lymphocytes, monocytes, eosinophils, and basophils
  - Descriptive summaries of raw values will be presented in a single table for the select measures of WBC, RBC, hemoglobin, hematocrit, platelets, and MPV.
  - Descriptive summaries of CFB values and Wilcoxon signed rank test results will be presented in a single table for the select measures of WBC, neutrophils, lymphocytes, monocytes, eosinophils, and basophils.
- **Chemistry:** blood glucose, BUN, creatinine, sodium, potassium, chloride, calcium, CO2, alkaline phosphatase, AST (SGOT), ALT (SGPT), total bilirubin, GGT, albumin, LDH, total cholesterol, total protein, and hs Troponin I (or hs Troponin T)

Results for select coagulation and hematology measures will also be provided in panels of spaghetti plots, with each panel corresponding to a single measure and incorporating 3 plots per row (1 plot for each patient cohort) and each plot presenting an overlay of the raw assessment results for individual patients through time. For each measure, 2 separate panels in total will be constructed. In the first panel (1 row x 3 columns and up to 1 page in length), individual patients will be represented without subgrouping. In the second panel (3 rows x 3 columns and up to 3 pages in length, given 1 row per page), line colors or patterns will be used to distinguish patients as belonging to Subgroup 1 or 2 (did or did not receive anticoagulant therapy; row 1), Subgroup 3 or 4 (did or did not receive platelet transfusion; row 2), and Subgroup 5 or 6 (did or did not receive any blood product transfusion other than platelets; row 3). Panels will be constructed for all measures listed below, given available data.

- Coagulation: INR, aPTT, D-dimer, fibrinogen, TAT, PF 1+2, TEG R time, TEG MA, TGA time to peak, and TGA thrombin peak height
- Hematology: WBC, hemoglobin, and platelets

Pertaining solely to the measure of WBC count, a single table will be produced to provide descriptive summary of the numbers and percentages of patients with abnormal results by visit and living status (Subgroup 7 vs. 8; see Section 6.6). Given the potential for lab normal ranges (and, thus, classification of WBC count results as abnormal) to differ across study sites, a second table will display the numbers and percentages of patients at different WBC count levels (defined using quantiles of raw WBC counts across all measurements, patients, and sites) by visit and living status. To facilitate visual examination of trend, this latter summary may also be presented within a supplementary clustered bar chart, line chart overlay, or panel of survival curves. Lastly, multiple data listings will be produced to disclose the details of sample collection and results for all clinical laboratory assessments performed per patient.

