## **1.11 Inclusion /Exclusion Criteria**

### ***1.11.1 Inclusion Criteria***

1. Males and non-pregnant/non-breastfeeding females at least 18 - 74 years of age.
2. Ability to comprehend the study procedures and signed informed consent.
3. Diagnosed with any the following: acute leukemia (ALL or AML), myelodysplasia, aplasia, and/or therapy (chemotherapy or radiation) induced bone marrow aplasia or hypoplasia with thrombocytopenia (see #6 below) for a minimum of 2 days. Patients who have received either autologous or allogeneic bone marrow transplant, peripheral, or cord blood stem cells may be enrolled if they do not have chronic or acute graft-versus-host disease (GVHD).
4. WHO Grade 1 (subset) or 2 bleeding or at risk for same within 4 weeks of screening. Subset of patients with Grade 1 bleeding are those who have either epistaxis, hematuria, oral petechiae, oropharyngeal bleeding, or bleeding at invasive or other wound sites. WHO Grades 0, 3 or 4 are not inclusion criteria for eligibility.
5. If not hospitalized, willing to be observed in a clinic up to the 6-hour post-infusion time point. Patients may be admitted and observed in the hospital overnight at the discretion of the PI.
6. Thrombocytopenia with platelet count  $\geq 5,000/\mu\text{L}$  and  $\leq 70,000/\mu\text{L}$ .
7. Has permanent address and phone/email for contact and notifications, and available for the duration of the trial, which is expected to be a maximum of 8 weeks.
8. Agrees to not take any nonsteroidal inflammatory drugs within 5 days prior to infusion and during the 6 Day study follow-up period.
9. Agrees to not take any aspirin or aspirin containing drugs within 5 days prior to infusion and during the 6 Day study follow-up period.

10. Agrees to not take any COX-2 inhibitor drugs within 5 days prior to infusion and during the 6 Day study follow-up period.
11. Female patients must have a negative pregnancy test prior to enrollment and during study. Women who are postmenopausal for at least 1 year (>12 months since last menses) or are surgically sterilized do not require this test.

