### 3.3 Summary of Activities and Assessments

**Table 2 – Schedule of Activities and Assessments, Modified from CSP 2017-1 Table 4**

Evaluation	Initial Screen	Rescreen 	Day 1 (baseline) 	1-h post-infusion ±15 min	6-h post-infusion -1 or +2 h	Day 2 24-h post-infusion ±3 h	If hospitalized			Day 6 (+4 d)	Day 30 (+2 d) (via phone)
							Day 3	Day 4	Day 5		
Visit Number:	1	1A	2	3	4	5	6	7	8	9	10
Sign informed consent form	X										
Verbally reconfirm consent		X	X	X	X	X	X	X	X	X	X
Medical history and complete physical exam 	X										
WHO bleeding severity	X	X	X	X	X	X				X	
Abbreviated physical exam 		X	X	X	X	X				X	
Pregnancy test (female only)	X	X									
Concomitant medications 	X	X	X	X	X	X	X	X	X	X	
Record transfused blood products 	X	X	X	X	X	X	X	X	X	X	
Thrombosomes infusion			X								
Vital signs 	X	X	X	Prior to infusion, then every 15 ±5 min after start of infusion until 2 h. Continue every 1 h ±5 min until 4 h, then at 6 h and 24 h ±10 min post-infusion.						X	
Pulse oximetry			X	Monitor continuously during vital signs assessment; record at same time-points as vital signs.							
Monitor for AEs			X	Prior to infusion, then every 15 ±5 min after start of infusion until 2 h. Continue every 1 h ±5 min until 4 h, then at 6 h and 24 h ±10 min post-infusion. Continue daily monitoring until discharged or Day 6.				X	X	X	X 
12-lead EKG 	X		X 		X						
Hematology CBC 	X	X	X	X	X	X	Daily CBC, at minimum		X		
ABO group, Rh type	X										
Coagulation testing 	X	X	X	X	X	X					
Routine chemistry 			X		X	X					
Special chemistry 			X		X	X					
Draw archive sample 	X									X	

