**Table 3 – List of Nominal Visits and Time-Points**

Nominal Visit/Time-Point	Scheduled Study Day	Day/Time Window
Screening 	Days -28 to Day -1	Any time during Days -28 to Day -1
Baseline	Day 1	Any time pre-infusion during Day 1 
Thrombosomes Infusion	Day 1	None; represents time-point 0 and provides reference for nominal visits and time-points
1-hour post-infusion	Day 1	±15 minutes
6-hour post-infusion	Day 1	-1 to +2 hours
24-hour post-infusion	Day 2	±3 hours
Day 3 	Day 3	Any time during Day 3
Day 4 	Day 4	Any time during Day 4
Day 5 	Day 5	Any time during Day 5
Day 6	Day 6	+4 days (any time during Days 6-10)
Day 30	Day 30	+2 days (any time during Days 30-32)

 If the patient is not actively bleeding at the time of screening but bleeding occurs within 4 days (+6 hours) of initial screening, the patient will not be rescreened (just WHO bleeding severity and CBC assessments will be repeated). If the patient is not actively bleeding at the time of screening but bleeding occurs >4 days and within 4 weeks of initial screening, the patient will be wholly rescreened and, following verification of eligibility, then enrolled and infused.

 Baseline assessments may occur any time preceding infusion on Day 1, except for the assessments of WHO bleeding severity, CBC, and coagulation. These assessments will be required to occur within the 2 hours preceding infusion.

 Relevant only if the patient is hospitalized.

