#### **6.4 Missing Values**

For all patients enrolled and all activities and assessments performed, every effort will be made to achieve complete data collection. Imputation is not planned for missing data, other than for missing date/time values. The missing component(s) of incomplete dates (e.g. start or stop dates of TEAEs, concomitant medication use, events/conditions in medical history) will be assumed to be the most conservative value possible. For example, if the start date is missing the day value, then the first day of the month will be imputed for study day computations. If the end date is missing the day value, then the last day of the month will be imputed. A similar approach will be used for missing month and year components. For complete dates but missing start or end times, values marking the beginning of the day (00:00:00AM) or end of the day (23:59:59PM), respectively, will be imputed. Importantly, date/time imputation will be used for computational purposes only; actual data values (as they appear in the database) will be presented in all patient-level data listings. Patients who withdraw consent for study participation or are lost to follow-up will be included in data summaries and analyses to the point of last contact.

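### On Days 3-5 the raw hematology summaries cover only hospitalized patients, and no paired change from baseline is planned for platelets, hemoglobin, hematocrit, RBC or MPV

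*SAP*

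**What the plan says.** One of the primary endpoints in SAP 2.2.1 is "Statistics describing (and/or graphics showing) central tendency and variability in coagulation, hematology, and serum chemistry measures across patients at baseline and post-baseline time-points", described as "allowing for assessment of directional change in measures over time", by cohort and overall.

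For hematology, SAP 8.3 splits the measures between two tables.

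- **Raw values (Table 14.3.5.1):** "Descriptive summaries of raw values will be presented in a single table for the select measures of WBC, RBC, hemoglobin, hematocrit, platelets, and MPV".
- **Change from baseline with signed-rank tests (Table 14.3.5.2):** "for the select measures of WBC, neutrophils, lymphocytes, monocytes, eosinophils, and basophils".

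WBC is in both lists. Platelets, hemoglobin, hematocrit, RBC and MPV are only in the first.

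SAP Table 2 schedules a blood count for every patient at baseline, 1 h, 6 h, 24 h and Day 6. For Days 3-5 the entry is "Daily CBC, at minimum", in columns that apply to inpatients. SAP Table 3 lists Days 3, 4 and 5 as nominal visits, with the note "Relevant only if the patient is hospitalized". That note is keyed to Day 3, while Days 4 and 5 carry the baseline footnote, but Table 2 makes clear that all three days are conditional.

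Outpatients are eligible under Protocol 1.11.1: "If not hospitalized, willing to be observed in a clinic up to the 6-hour post-infusion time point". SAP 6.4 adds: "Imputation is not planned for missing data, other than for missing date/time values".

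Protocol 1.16 planned both the observed value and the change from baseline, with a significance test, for every laboratory test. SAP section 11, which sets out the most significant departures from the protocol, does not mention that this was dropped for five hematology measures.

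**The concern.** A reader following a row of Table 14.3.5.1 from 24 h through Days 3-5 to Day 6 would take it as the course of one cohort. It need not be. The set of patients can shrink after 24 h, shrink again with each discharge, and refill at Day 6. If those in hospital differ in level from those at home, the mean and median move although nobody's count has changed.

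The shift depends on each cohort's inpatient share, so cohorts with different discharge patterns could appear to respond differently to dose. Platelets and hemoglobin are the counts a reader will look at first for a platelet-derived product given to bleeding patients, and they are among the measures without a paired summary. The problem is specific to hematology: coagulation and chemistry are not scheduled on Days 3-5.

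**Working it through.** The plan states no figure on this point, so there is none to reproduce.

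**Inputs from the documents**
- 8 patients per cohort (SAP 4).
- Seven post-infusion count visits: 1 h, 6 h, 24 h, Days 3, 4, 5 and 6. Four are scheduled for all patients; three are for inpatients only.
- Platelet count at entry 5,000 to 70,000/µL (Protocol 1.11.1).

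**Inputs that must be assumed**
- *f*, the share of the cohort in hospital on Days 3-5.
- The difference between inpatient mean *mI* and outpatient mean *mO*.
- Days 3-5 appear as columns in Table 14.3.5.1. This follows from the nominal visits in SAP Table 3, but no table shell is given.

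**Formula, with no change in any patient**
- All-patient mean = *f* x *mI* + (1 - *f*) x *mO*
- Days 3-5 mean = *mI*
- False shift = *mI* - [*f* x *mI* + (1 - *f*) x *mO*] = (1 - *f*) x (*mI* - *mO*)

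**Platelets: false shift in the cohort mean (per µL)**

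| In hospital | Inpatients 5,000 lower | 10,000 lower | 15,000 lower |
|---|---|---|---|
| 3 of 8 | -3,125 | -6,250 | -9,375 |
| 4 of 8 | -2,500 | -5,000 | -7,500 |
| 6 of 8 | -1,250 | -2,500 | -3,750 |
| 8 of 8 | 0 | 0 | 0 |

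The sign follows the difference. With 4 of 8 in hospital and inpatients 5,000/µL *higher*, the shift is 0.5 x 5,000 = +2,500/µL.

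**Hemoglobin.** With inpatients 0.5 to 1.5 g/dL lower, the smallest shift is 0.25 x 0.5 = 0.125 g/dL (6 of 8) and the largest is 0.625 x 1.5 = 0.94 g/dL (3 of 8), both downward.

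**Between cohorts.** Take the same 10,000/µL difference, with 3 of 8 in hospital in one cohort and 6 of 8 in another. The false shifts are -6,250 and -2,500/µL, so the cohorts appear to differ by 3,750/µL with no dose effect at all.

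**Effect of pairing.** Suppose four inpatients have 12,000, 14,000, 16,000 and 18,000/µL (mean 15,000), four outpatients have 30,000, 34,000, 36,000 and 40,000/µL (mean 35,000), and no count changes.

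| Visit | n | Raw mean | Mean paired change |
|---|---|---|---|
| Baseline | 8 | 25,000 | - |
| 1 h, 6 h, 24 h | 8 | 25,000 | 0 |
| Days 3-5 | 4 | 15,000 | 0 |
| Day 6 | 8 | 25,000 | 0 |

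The raw column shows a fall and a recovery. The paired column correctly shows nothing. Pairing has one limit: on Days 3-5 it still describes inpatients only, so it removes the artefact of level but does not say how outpatients changed on those days.

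**The case against.** A reader might infer that the whole directional-change endpoint reports who stayed in hospital rather than what followed infusion. The documents do not support that. Four of the seven post-infusion visits are scheduled for everyone, and comparisons among them are unaffected by hospital status.

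Nor can one say that the table *will* show a fall. The documents give no inpatient share and no difference in counts, and they do not say that discharge depends on counts. Protocol 1.9.2.2 allows transfusion without limit when bleeding persists or worsens, which could raise inpatient counts. Protocol 1.9.2 describes the patients as hospitalized, so the share could be close to 1 and the effect close to zero. It is also tempting to set the 5,000/µL result beside the worsening cut-off in SAP 9.1, but that cut-off classifies one patient's change and is no benchmark for a cohort mean.

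Two further inferences fail. The planned signed-rank tests are not distorted in this way: they are paired, SAP 6.3 sets the change to missing when either value is missing, and they cover only WBC and the differential. The three-data-point rule in SAP 8.3 decides which measures have enough data to be summarized; it is not written as a rule for displaying a visit.

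The SAP also has safeguards, each of them partial.

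- **Printed n** (SAP 6.9) shows that membership changed, not what the change did. The median and interquartile range move with membership too.
- **Individual line plots** cover hemoglobin, platelets and WBC, and the endpoint admits graphics. They give no summary statistic and omit hematocrit, RBC and MPV.
- **Shift tables** by visit hide movement within a category, which matters when every patient enters with a low platelet count. Their Days 3-5 rows cover the same inpatients.
- **SAP 9.1 categories** are secondary, omit RBC and MPV, and count a patient who both improves and worsens as improved. Inpatients have more counts and so more chances to cross a threshold.

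Finally, the consequence is limited. No between-cohort hematology test is planned, the stopping rules do not use this table, and the monitoring committee's listed hematology item is a data listing. That stands, and it keeps the point to interpretation of the report.

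**Conclusion.** The point holds for Days 3-5, three of seven post-infusion visits. There the raw summaries of all six measures describe a different set of patients from the other columns. For five of them the SAP plans no paired change to separate membership from real change, although the protocol did.

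Size and direction are unknown. Under the assumed shares of 3/8 to 6/8 and inpatient platelets 5,000-15,000/µL lower, the false shift is a fall of 1,250 to 9,375/µL. It vanishes if all patients remain in hospital and reverses if inpatients have higher counts. The existing displays reduce the problem without removing it. This is a modest weakness in presentation, worth correcting because the correction costs so little.

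**What to change.** In SAP 8.3:

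1. Base cohort-level statements about direction of change on the visits scheduled for all patients: baseline, 1 h, 6 h, 24 h and Day 6.
2. In Table 14.3.5.1, move Days 3-5 to a separate block labelled as hospitalized patients only. For each day give n and the baseline and 24-hour values of those same patients.
3. Add paired change from baseline for platelets, hemoglobin, hematocrit, RBC and MPV to Table 14.3.5.2, as Protocol 1.16 planned, with Days 3-5 labelled in the same way.

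The signed-rank tests already planned for WBC and the differential need no restriction.

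The cost is SAP wording and table layout, using data already collected. The tables become longer, and Days 3-5 leave the main trend.
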